**Table 6: Adverse Event Classification**

Grade	Classification
1	Mild adverse event; did not require treatment
2	Moderate adverse event; resolved with treatment
3	Severe adverse event; inability to carry on normal activities; required professional medical attention
4	Life-threatening or permanently disabling adverse event
5	Fatal adverse event

The relationship to study treatment for each AE will be classified as 'Unrelated', 'Possibly Related', 'Probably Related', or 'Definitely Related'. AEs classified as 'Possibly', 'Probably' or 'Definitely' related will be analyzed as 'Related' in the AE summaries. Data listings, patient narratives, etc. will present the relationship to study treatment as collected on the CRF.

### **11.3.2. Tabulations of Treatment-Emergent Adverse Events**

Adverse event data will be summarized and presented using primary MedDRA SOCs and PTs according to the version of the MedDRA coding dictionary used for the study at the time of database lock. The actual version of the MedDRA coding dictionary used will be noted in the clinical study report. The SOCs will be presented in alphabetical order and the PTs will be presented in alphabetical order within each SOC.

Adverse events will be presented overall and by actual dose received and age group.

#### **11.3.2.1. Adverse Event Overview**

An overview of AEs will be presented by the actual treatment received overall and by dose and age group consisting of the number and percentage of patients experiencing at least one event for the following AE categories:

- Any TEAEs
- TEAEs related to study treatment
- TEAEs of Grade III (severe) severity or higher
- Serious TEAEs
- Serious TEAEs related to study treatment
- TEAEs leading to discontinuation of patient from study
- TEAEs leading to death

#### **11.3.2.2. Adverse Events by SOC and PT**

The following summaries of AEs will be generated:

- Incidence of TEAEs

- Incidence of TEAEs related to study treatment
- Incidence of serious TEAEs
- Incidence of serious TEAEs related to study treatment
- Incidence of TEAEs in Grade 2 (moderate) or Grade 3 (severe) severity
- Incidence of TEAEs in Grade 3 (severe) severity
- Incidence of TEAEs in Grade 3 (severe) or Grade 4 (life-threatening) severity
- Incidence of TEAEs leading to discontinuation of patient from study
- Incidence of TEAEs leading to death
- Incidence of TEAEs related to study treatment and leading to death
- Incidence of TEAEs leading to concomitant medication use
- Incidence of non-serious TEAEs

For all AE summaries, the number and percentage of patients experiencing TEAEs will be tabulated according to SOC and PT for each actual drug/product received. Patients reporting more than one AE for a given PT will be counted only once for that term (most severe incident for the severity tables and most related incident for the relationship tables), although each event will be counted individually. Patients reporting more than one AE within an SOC at a study period will be counted only once for that SOC.

A listing by dose of TEAEs grouped by SOC and PT with patient numbers will be created.

#### **11.3.2.3. Adverse Events by PT**

The number and percentage of patients experiencing TEAEs will be tabulated according to PT and sorted by overall frequency. Similar summaries will be provided for Grade 3 and Grade 4 TEAEs and TEAEs related to study drug/product.

#### **11.3.2.4. Adverse Events of Special Interest**

The following specific TEAEs of special interest, which are primarily defined by using Standardized MedDRA queries (SMQ), will be summarized:

- Hepatotoxicity, identified via the following SMQ:
  - Hepatic disorders (SMQ)
- Thrombocytopenia, identified via the following CMQ:
  - Transient thrombocytopenia (CMQ)
- Cardiac events, identified via the following SMQs:
  - Ischemic heart disease (SMQ)
  - Cardiomyopathy (SMQ)
  - Cardiac arrhythmias (SMQ)

- Embolic and thrombotic events (SMQ)
- Myocardial infarction (SMQ)
- Thrombotic microangiopathy, identified via the following approach:
  - Criteria #1: cases with **any one** of the following PTs: thrombotic microangiopathy **OR** haemolytic uraemic syndrome **OR** atypical haemolytic uraemic syndrome
  - Criteria #2: cases with **at least one PT** from **EACH** of the following SMQs representing thrombocytopenia, hemolysis and relevant renal events respectively:
    - Haematopoietic thrombocytopenia (SMQ)
    - Haemolytic disorders (SMQ)
    - Acute renal failure (SMQ) **OR** Renovascular disorders (SMQ)
- Sensory abnormalities suggestive of ganglionitis, identified via the following CMQ:
  - DRG Cell Inflammation (CMQ)

For each AE of interest category, the number and percentage of patients experiencing at least one TEAE in the search for the event of interest will be presented overall and by actual dose received and age group. AEs of interest will be summarized by SOC and PT overall, by actual dose received, and age group.

#### 11.3.2.5. Adverse Events by Maximum Severity

Treatment-emergent adverse events will be summarized by maximum CTCAE grade of each PT. Each PT will be assigned to a grade level, as assessed by the investigator, based on the CTCAE version 4.03 for grading severity of AEs. If a patient has an AE with an unknown grade, then the patient will be counted in the severity grade level category of "unknown", even if the patient has another occurrence of the same event with a grade present.

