### **6.3. Missing Data**

Patients are allowed to withdraw from the study at any time. Analysis of quantitative and categorical variables will include data from patients with non-missing values. For continuous variables, a MMRM model may be used for the comparison between AVXS treated patients and the matching PNCR cohort.

Imputation of missing or incomplete dates will only be performed on AEs and concomitant medications for determining the timing relative to the dose of study product unless otherwise specified. The rules of imputation of missing dates are specified in Table 1 and Table 2. Partial or missing dates will be listed as recorded in the electronic case report form (eCRF). All imputed dates will be no earlier than the patients' birth date.

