**Table 2: Rules of Date Imputation: Post-Dose Assessments**

Partial Missing Start Date	Imputed Start Date
Missing month and day, but the year is present	Date of dose
Missing day, but year and month are present	First day of that month or dose date if the year and month are the same as the year and month of dose date
Missing month, but year and day are present	Month of dose

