#### 11.3.2.6. Adverse Events by Maximum Relationship

Treatment-emergent adverse events will be summarized by maximum relationship of each PT to study product (AVXS-101), as assessed by the investigator. Events with an assessment of 'Possibly Related', 'Probably Related' or 'Definitely Related', will be summarized as 'Related' in the table. Events with an assessment of 'Unrelated' will be summarized as 'Unrelated' in the table. If a patient has more than one occurrence of the same event, and one is 'related' and the other is 'unrelated', then the 'related' event is considered to be the one having the maximum relationship to study drug. If a patient has an AE with unknown relationship, then the patient will be counted in the relationship category of "unknown". The only exception is if the patient has another occurrence of the same AE with a relationship present. In this case, the patient will be counted under the maximum relationship category.

For the final analysis tables (i.e., after database lock of the study), just the two relatedness categories ("Related", "Not Related") will be presented.

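### SAP maximum-severity table drops a known grade when another occurrence is ungraded, and Table 2's missing-month rule can date a post-dose adverse event before dosing (minor)

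*SAP*

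**What the plan says.** **Severity.** SAP 11.3.2.5 summarises treatment-emergent adverse events (TEAEs) by the highest CTCAE grade for each preferred term. A patient with an ungraded occurrence is counted as unknown for that term, "even if the patient has another occurrence of the same event with a grade present". SAP 11.3.2.2, which covers all AE summaries, counts a patient with repeated events once, using the "most severe incident for the severity tables and most related incident for the relationship tables". SAP 11.3.2.6 also has an unknown category for relationship, but lifts it when another occurrence has a value: "The only exception is if the patient has another occurrence of the same AE with a relationship present". Separate counts appear in 11.3.2.1 ("TEAEs of Grade III (severe) severity or higher"), in the Grade 3 and Grade 3-4 tables of 11.3.2.2, and in 11.3.2.3 ("Similar summaries will be provided for Grade 3 and Grade 4 TEAEs").

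**Dates.** SAP 6.3 imputes partial AE dates for "determining the timing relative to the dose of study product". The floor it states is: "All imputed dates will be no earlier than the patients' birth date". Table 2 is titled "Rules of Date Imputation: Post-Dose Assessments". Its three rows work as follows:

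- Year only: the dose date.
- Day missing: the first of the recorded month, or the dose date if month and year match those of dosing.
- Month missing: the month of dose, with the recorded day and year kept.

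SAP 11.3.1 defines a TEAE as an event that begins or worsens after the injection. For incomplete onset dates it then tests whether the imputed onset falls after the date and time of injection.

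**The concern.** A maximum-grade table should show the worst grade known. Under 11.3.2.5, a child with one Grade 4 and one ungraded occurrence of the same term leaves the Grade 4 line, so a reader of that table alone misses a known severe event. Other tables in the same report would still show it. The primary safety objective rests on the incidence and severity of AEs (SAP 3.1.1), and the dose groups are very small, so such a disagreement would be noticed and would need explaining.

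The date rule matters for a different reason. A record handled under Table 2 is taken to be post-dose, yet the missing-month row can return a date before dosing. If TEAE status is programmed from that date, the event drops out of the TEAE tables.

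**Working it through.** The plan gives no figure to reproduce, so the check applies the rules as written.

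**1. Severity rule.** Occurrences of one preferred term in one child:

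| Grades recorded | SAP 11.3.2.5 | Maximum known grade |
|---|---|---|
| 3 | 3 | 3 |
| 3, none | unknown | 3 |
| 4, none | unknown | 4 |
| 5, none | unknown | 5 |
| none | unknown | unknown |

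The two rules differ only when graded and ungraded occurrences of the same term coexist in one child. An event under another term keeps its grade. The ungraded rule is written only for 11.3.2.5. The Grade III-or-higher overview row and the Grade 3-4 tables need one qualifying event, so they still count the child.

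**2. Missing-month rule.** The imputed onset is the recorded year, the dose month and the recorded day. With dosing on day D of a month, a valid imputed date precedes dosing exactly when the recorded year is the dose year and the recorded day is below D.

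Example, with illustrative dates: dosing on 20 November 2018, onset recorded as day 5, month missing, 2018.

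- Imputed onset: 5 November 2018, 15 days before dosing.
- Only post-dose date that fits the record: 5 December 2018, 15 days after dosing.
- In the same way, all 19 dates from 1 to 19 December 2018 map to 1 to 19 November 2018.
- Day 31 maps to 31 November, which does not exist.

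The condition was checked over every dosing day in 2018-2020 (365 + 365 + 366 = 1,096) with onset 0 to 449 days later, giving 1,096 × 450 = 493,200 cases. The rule gave a valid date in 487,689 of them, and the condition held in every one. The other 493,200 − 487,689 = 5,511 cases (1.1%) gave a date that does not exist, and the SAP does not say how to handle them.

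**3. Replacement date rule.** Taking the earliest valid calendar date that fits the recorded parts and is not before dosing was run on the same 493,200 cases. It never fell before dosing and never fell after the true onset. It gives 5 December 2018 for the example and 31 December 2018 for the day-31 record.

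**4. Ties.** Year-only dates, and missing-day dates in the dosing month, are set to the dose date. SAP 11.3.1 compares the onset with the date and time of injection, but an imputed date carries no time. The SAP does not say how equality is resolved. This is an ambiguity, not a demonstrated loss.

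**The case against.** **An unknown grade is honest.** If one occurrence is ungraded, the true maximum is uncertain unless another is Grade 5, and 11.3.2.2 does not say what to do about a missing grade. So 11.3.2.5 can be read as the specific rule. This stands in part: the two sections are not in flat contradiction on missing grades. But the known grade is a lower bound on the true maximum, and the unknown category discards it. A footnote keeps the uncertainty visible without hiding a severe event. The opposite treatment of relationship in 11.3.2.6 is unexplained.

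**The event may still be a TEAE.** This stands. One might infer that a pre-dated event is lost under every reading. The documents do not support that: 11.3.1 opens with events that begin or worsen after injection, so one that later worsens can qualify. Non-serious AEs are collected only from the injection onward (SAP 4.4), so a pre-dose date on one would look wrong on review. What remains is that the event fails the imputed-onset test as written.

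**The primary safety endpoints are untouched.** One might infer that the Grade 3-or-higher endpoint is understated. That is not shown. SAP 4.4 defines the endpoints on any AE, no passage says the TEAE overview reports them, and the severity rule does not reach the overview. A date loss would change a patient-level proportion only if the child had no other qualifying event.

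**Few records can be affected.** Protocol 13.3 requires onset and intensity for every AE, and a record with day and year but no month is unusual. Listings keep partial dates as recorded (SAP 6.3). All of this stands and is why the point is minor.

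**Conclusion.** Both rules give the wrong output when their conditions are met, and both follow from the SAP text. The severity rule can make the maximum-severity table disagree with the Grade III-or-higher row and the Grade 3-4 tables. The missing-month rule can put a post-dose onset before dosing, or produce an impossible date.

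The size cannot be estimated: the documents give no count of ungraded or partly dated AEs, and it may be zero. For scale only, one child is 1/12 = 8.3% of a planned Dose B age group, 1/4 = 25% of the four children treated in Cohort 3 (SAP 2.2.1), and 1/3 = 33% of Cohort 1. These are shares of a denominator, not estimates of bias.

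The date conclusion assumes that Table 2 is applied literally and TEAE status is taken from the imputed onset. Efficacy, power and the significance level are not involved. This is an improvement the sponsor could make, not a fault that undermines the safety analysis.

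**What to change.** - **SAP 11.3.2.5:** assign the maximum known grade, footnote patients who also have an ungraded occurrence of that term, and reserve the unknown category for terms with no graded occurrence.
- **SAP Table 2:** impute the earliest valid calendar date that fits the recorded parts and is not before the dose date. If no such date exists, the record cannot be post-dose as entered and should be queried.
- **SAP 11.3.1:** treat an imputed onset equal to the dose date as treatment-emergent unless the record shows that it was pre-dose. The exception is needed because SAEs are collected from consent (SAP 4.4).

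The cost is a short SAP revision and minor reprogramming with its quality control; no new data are needed. SAP 6.0 is final and an additional analysis was already run after the last Cohort 2 patient's 12-month visit (SAP 2.2.2), so any affected record would also have to be reconciled with those tables. A count of ungraded and partly dated AEs would show whether that arises.

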#### 11.3.2.6. Adverse Events by Maximum Relationship

Treatment-emergent adverse events will be summarized by maximum relationship of each PT to study product (AVXS-101), as assessed by the investigator. Events with an assessment of 'Possibly Related', 'Probably Related' or 'Definitely Related', will be summarized as 'Related' in the table. Events with an assessment of 'Unrelated' will be summarized as 'Unrelated' in the table. If a patient has more than one occurrence of the same event, and one is 'related' and the other is 'unrelated', then the 'related' event is considered to be the one having the maximum relationship to study drug. If a patient has an AE with unknown relationship, then the patient will be counted in the relationship category of "unknown". The only exception is if the patient has another occurrence of the same AE with a relationship present. In this case, the patient will be counted under the maximum relationship category.

For the final analysis tables (i.e., after database lock of the study), just the two relatedness categories ("Related", "Not Related") will be presented.

## 11.4. Laboratory Evaluations

### 11.4.1. Variables and Criteria Defining Abnormality

*Hematology* variables include: Hematocrit, Hemoglobin, Red Blood Cells, White Blood Cells, Platelets, Neutrophils, Lymphocytes, Monocytes, Basophils, and Eosinophils.

*Clinical Chemistry* variables include: AST, ALT, Gamma glutamyl transferase (GGT), Alkaline phosphatase, Total creatinine kinase, Direct bilirubin, Serum total bilirubin, Glucose, Electrolytes (Sodium, Potassium, Chloride, CO2), Albumin, Creatinine, BUN, CK-MB, and Troponin I.

*Coagulation* variables include: Prothrombin time, Partial prothrombin time, and International normalized ratio

*Urinalysis* variables include: Color, Clarity/turbidity, pH, Specific gravity, Glucose, Ketones, Nitrites, Leukocyte esterase, Bilirubin, Blood, Protein, Red blood cells, White blood cells, Squamous epithelial cells, Casts, Crystals, Bacteria, Yeast

*Virus Serology* variables include: Human immunodeficiency virus, Hepatitis B, Hepatitis C, and Zika virus

*Capillary Blood Gas* variables include: pH, pCO2, pO2, TCO2

*Immunology* variables include: Serum antibody to AAV9 (Anti-AAV9), Serum antibody to SMN (Anti-SMN Ab), and Interferon Gamma (IFN- $\gamma$ ) ELISpot measurement of T-cell response to AAV9 and SMN.

The Criteria for Potentially Clinically Significant (PCS) values are generally based upon CTCAE version 4.03 criteria for Grade 2 or higher AEs. Age-related differences in normal ranges of some analytes in pediatric (vs adult) populations were taken into account in defining PCS Values.

The Criteria for PCS Laboratory Findings are maintained outside of this SAP.

### 11.4.2. Statistical Methods

Clinical laboratory tests at each scheduled visit will be summarized overall and by actual dose received and age group. The baseline value will be the last measurement on or before the day of the injection of study product. Mean changes from baseline to each post-baseline visit will be summarized for each protocol-specified hematology, clinical chemistry, coagulation, and capillary blood gas laboratory parameter with the baseline mean, visit mean, change from baseline mean, standard deviation, minimum, maximum, and median.

Immunology and virus serology data will be summarized using descriptive statistics appropriate for categorical variables (i.e. number and percentage of patients with each reported result at each visit). Urinalysis data will only be presented in listings.

Chemistry, hematology, and coagulation laboratory data values will be categorized as low, normal, or high based on normal ranges of the laboratory used in this study. Shift tables from baseline to minimum value, maximum value, and final treatment values will be created. The shift tables will cross tabulate the frequency of patients with baseline values below/within/above the normal range versus minimum/maximum/final values below/within/above the normal range.

The number and percentage of patients with post-baseline values meeting the specified criteria for PCS laboratory values will be summarized overall and by actual dose received and age group. A post-baseline value must be more extreme than the baseline value to be considered a PCS finding. A listing will be provided to present the entire set of lab values for a patient for the parameter meeting PCS criteria during treatment.

For hemoglobin and the liver function enzyme (LFE) tests of ALT, AST, and alkaline phosphatase, the number and percentage of patients in each age/dose group with a maximum CTCAE Grade of 1, 2, 3, or 4 (as defined by the central laboratory and based on CTCAE v4.03) at any post-baseline visit (regardless of the baseline value) through the end of study will be summarized. All LFE tables will include summary rows for the number and percentage of patients with at least Grade 2 and at least Grade 3 laboratory abnormalities. The hemoglobin table will include a summary row for the number and percentage of patients with a Grade 3 laboratory abnormality. Accompanying listings of all ALT, AST, total serum bilirubin, direct bilirubin, and alkaline phosphatase will be created for any patients who had at least a Grade 3 ALT, AST, or alkaline phosphatase value. A listing of hematology results will be provided for patients with hemoglobin abnormalities.

The number and percentage of patients meeting the following criteria will be summarized overall and by dose and age group:

- ALT >3x ULN, ALT >5x ULN, ALT >10x ULN, ALT >20x ULN
- AST >3x ULN, AST >5x ULN, AST >10x ULN, AST >20x ULN
- ALT or AST >3x ULN, ALT or AST >5x ULN, ALT or AST >8x ULN, ALT or AST >10x ULN, ALT or AST >20x ULN
- Total bilirubin >2x ULN, Total bilirubin >3x ULN
- ALT or AST >3x ULN and Total bilirubin >2x ULN
- ALT or AST >3x ULN and Total bilirubin >2x ULN and Alkaline phosphatase  $\geq$ 2x ULN
- ALT or AST >3x ULN and Total bilirubin >2x ULN and Alkaline phosphatase <2x ULN

A patient or event will be counted if the post-baseline laboratory values meet the above criteria regardless of the baseline laboratory value (i.e., the post-baseline laboratory value does not need to be worse than the baseline laboratory value). For the last three combination categories, the values do not need to have been collected at the same assessment. For patients meeting any elevation criterion, a corresponding listing of all ALT, AST, alkaline phosphatase, and total, direct, and indirect bilirubin values will be provided.

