Nonclinical cardiovascular toxicity findings that could potentially be relevant to the clinical use of AVXS-101 have been reported in 2 mouse toxicology studies of AVXS-101. Similar findings were reported in both studies. Findings in the ventricles of the heart were comprised of inflammation, edema and fibrosis. Primary findings in the atrium of the heart were thrombosis and inflammation. The underlying mechanism of these findings and the translatability of the observed findings in mice to primates are not known at this time.

The available clinical cardiovascular safety data have not provided evidence for a cardiovascular safety problem in humans. As of the last update to the Investigator's Brochure (v5), there have

been no cardiovascular AEs that have been judged to be related to AVXS-101 in the clinical studies.

A transient decrease in platelet counts has been observed with both IV and less frequently with IT administration. The majority of values remained above the lower limit of normal. Decreases were clinically asymptomatic and transient.

This risk can be effectively managed through monitoring platelet counts for 1 month following dosing, and appropriate prednisolone (or an equivalent corticosteroid in countries where prednisolone is not available) use.

Preclinical data indicate that in most cases, DNA delivered by recombinant AAV vectors predominantly persists as extrachromosomal elements (episomes) rather than integrating into host cell genomes ([McCarty 2004](#)). Although AVXS-101 is also not anticipated to integrate into the host cell genome as described above, the long-term consequences of administering AAV viral vectors to humans are not yet fully understood. This is in contrast to wtAAV, also nonpathogenic, which has the ability to stably integrate into the host cell genome at a specific site (designated AAVS1) in the human chromosome 19 ([Kotin 1990; Surosky](#) ). Since the AVXS-101 product uses AAV9 with all of the wtDNA removed from the capsids, except for the inverted terminal repeats (ITRs), the potential risk of incorporation of AVXS-101 into the patient chromosomal DNA is thought to be significantly reduced.

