#### 9.2.1. Prophylactic Administration of Prednisolone

An antigen specific T-cell response to the AAV vector was observed in the ongoing Phase 1 clinical study investigating AVXS-101 treatment via IV infusion. This is an expected response between 2-4 weeks following gene transfer. One possible consequence to such antigen specific T-cell response is clearance of the transduced cells and loss of transgene expression.

In an attempt to dampen the host immune response to the AAV based therapy, patients will receive prophylactic prednisolone (glucocorticoid) (approximately 1 mg/kg/day) 24 hours prior to AVXS-101 dosing. Treatment will continue for approximately 30 days in accord with the following treatment guideline:

- Until at least 30 days post-injection: 1 mg/kg/day
- Weeks 5 and 6 post-injection: 0.5 mg/kg/day
- Weeks 7 and 8 post-injection: 0.25 mg/kg/day
- Week 9 post-injection prednisolone discontinued

Liver function testing should guide each step of the taper, and liver function tests should be checked prior to prednisolone discontinuation. If the GGT, AST or ALT values are  $\geq 2 \times$  ULN, then the present dose of prednisolone will be adjusted as needed until the GGT, AST, and ALT values decrease below threshold, at which point the taper may continue. Liver function tests

should also be checked approximately 2 weeks after the taper has concluded and prednisolone has been discontinued to evaluate for rebound elevation of GGT, AST or ALT levels. Variance from these recommendations will be at the discretion of the Investigator based on potential safety issues for each patient. If another glucocorticoid is used in place of prednisolone by the Investigator, similar considerations should be taken into account after 30 days and tapered as appropriate and at the discretion of the Investigator.

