#### 11.4.3. Drug-Induced Liver Injury

Drug-induced liver injury (DILI) has been the most frequent single cause of safety-related drug marketing withdrawals and as such with this pediatric population (SMA patients) and unique intervention (gene therapy), the Sponsor took care to assess hepatic test results as drugs can cause liver injuries by many different mechanisms. Severe DILI cases rarely have been seen in drug development programs of significantly hepatotoxic drugs that do cause such injury. Evidence of hepatocellular injury is thus a necessary, but not sufficient, signal of the potential to cause severe DILI (note, however, that the drugs causing hepatic injury through mitochondrial toxicity may not cause early hepatotoxicity).

It is possible that although a drug may not cause severe liver injury, it could still result in laboratory evidence of mild, transient hepatic injury, with leakage of liver enzymes and the appearance in serum of elevations in aminotransferase activities to levels of 3, 5, and sometimes greater than 5 times the ULN. The liver enzyme data was evaluated according to these criteria and according to Hy's Law.

A finding of ALT elevation, usually substantial, seen concurrently with bilirubin  $> 2 \times \text{ULN}$ , identifies a drug likely to cause severe DILI (fatal or requiring transplant) at a rate roughly 1/10 the rate of Hy's Law cases. It is critical to rule out other causes of injury (e.g., other drugs or viral hepatitis) and to rule out an obstructive basis for the elevated bilirubin, so that alkaline phosphatase (ALP) should not be substantially elevated. In all cases to date, the small number of Hy's Law cases has arisen on a background of an increased incidence of more modest signs of hepatocellular injury (e.g., greater incidence of  $3 \times \text{ULN}$  elevations in ALT than seen in a control group).

Briefly, Hy's Law cases have the following three components:

- The drug causes hepatocellular injury, generally shown by a higher incidence of 3-fold or greater elevations above the ULN of ALT or AST than the (nonhepatotoxic) control drug or placebo.
- Among study patients showing such AT elevations, often with ATs much greater than  $3 \times \text{ULN}$ , one or more also show elevation of serum Total Bilirubin (TBL) to  $> 2 \times \text{ULN}$ , without initial findings of cholestasis (elevated serum ALP).

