- No other reason can be found to explain the combination of increased AT and TBL, such as viral hepatitis A, B, or C; preexisting or acute liver disease; or another drug capable of causing the observed injury.

A listing of patients meeting the ALT  $\geq 3 \times \text{ULN}$  and TBL  $\geq 2 \times \text{ULN}$  will be produced.

For patients enrolled in this study these criteria will be assessed in order to determine both general LFE changes according to change from baseline and over course of study. In addition, changes in ALT or AST relative to Total Bilirubin will be assessed to determine whether a signal related to DILI has occurred in any individual or group of patients.

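### The Hy's Law listing selects on ALT alone, against the SAP's own ALT-or-AST rule, and the laboratory grade tables omit platelets and GGT, so their Grade 3+ counts by dose are not shown

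*SAP*

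**What the plan says.** **Grade tables.** SAP 11.4.2 gives the number and percentage of children at each maximum CTCAE grade, by age and dose group, "For hemoglobin and the liver function enzyme (LFE) tests of ALT, AST, and alkaline phosphatase". The liver tables have summary rows for at least Grade 2 and at least Grade 3. On the hematology side, "A listing of hematology results will be provided for patients with hemoglobin abnormalities"; no platelet value triggers that listing. Platelets are nonetheless a planned variable: SAP 11.4.1 lists "Hematocrit, Hemoglobin, Red Blood Cells, White Blood Cells, Platelets, Neutrophils" among others, and it lists GGT under clinical chemistry.

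**Liver rows and listings.** SAP 11.4.2 also counts, by dose and age group, ALT and AST above multiples of ULN starting at 3 ×, bilirubin above 2 × and 3 ×, and the combination of ALT or AST above 3 × with bilirubin above 2 ×. It plans two liver listings, one triggered by a Grade 3 ALT, AST or alkaline phosphatase value and one by any elevation criterion. GGT is in none of these rows and in neither listing.

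**Hy's Law.** SAP 11.4.3 describes the first component of a Hy's Law case as "3-fold or greater elevations above the ULN of ALT or AST". The output it then plans is worded "A listing of patients meeting the ALT" at or above 3 × ULN with total bilirubin at or above 2 × ULN. AST is not a selection variable there.

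**Why these tests matter to the trial.** Protocol 5.5 states: "A transient decrease in platelet counts has been observed with both IV and less frequently with IT administration". Protocol 13.1.3 names thrombocytopenia as an example of an adverse event of special interest, and SAP 11.3.2.4 gives it a dedicated search. GGT is an exclusion test (Protocol 8.2, criterion 19), part of the liver panel added at Days 44 and 72 (Protocol Table 3), and a taper criterion: "If the GGT, AST or ALT values are" at least 2 × ULN, the taper waits (Protocol 9.2.1).

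**The concern.** There are two separate weaknesses.

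First, the listing in 11.4.3 is the output a reader would open to look for Hy's Law candidates. Because it screens on ALT alone, it can disagree with the count in 11.4.2 and with the definition a few lines above it. The two outputs can then name different children, and the one labelled for the purpose is the narrower.

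Second, Grade 3 is the severity at which this trial acts. Protocol 12.1.1 defines dose-limiting toxicity by related Grade III events, and Protocol 12.1.2 halts enrollment for certain related Grade III or higher events, a rule that takes in important laboratory findings. Safety while finding the optimal dose is a primary objective (Protocol 6.1). For platelets and GGT, no laboratory table shows how many children reached Grade 3 at each dose.

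**Working it through.** No sample size or power figure is involved, so the check sets each planned output against each test.

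| Planned output | Platelets | GGT | AST |
|---|---|---|---|
| Maximum CTCAE grade by dose (SAP 11.4.2) | no | no | yes |
| Multiple-of-ULN rows by dose (11.4.2) | not applicable | no | yes |
| Listing triggered by grade or abnormality (11.4.2) | only if hemoglobin is abnormal | no | yes |
| Listing for any elevation criterion (11.4.2) | not applicable | no | yes |
| Visit summaries by dose (11.4.2) | yes | yes | yes |
| Shift tables, low/normal/high (11.4.2) | yes | yes | yes |
| PCS count by dose, with listing (11.4.2) | if the external criteria cover it | if the external criteria cover it | if the external criteria cover it |
| Special-interest event tables by dose (11.3.2.4) | if reported as an AE | if reported as an AE | if reported as an AE |
| Selection for the Hy's Law listing (11.4.3) | not applicable | not applicable | no |

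**Hy's Law listing, worked cases (multiples of ULN).**

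- AST 4, ALT 2.5, bilirubin 2.5. Row in 11.4.2: AST 4 > 3 and bilirubin 2.5 > 2, so the child is counted by dose and appears in the any-criterion listing. Listing in 11.4.3: ALT 2.5 < 3, so the child is absent. Whether this is a Hy's Law case also depends on alkaline phosphatase and on other causes, so the child is a candidate only.
- ALT exactly 3, bilirubin exactly 2. Listing in 11.4.3: 3 ≥ 3 and 2 ≥ 2, so listed. Row in 11.4.2: 3 > 3 is false, so not counted. This is an edge case, but it shows that the signs differ.
- With selection on ALT or AST ≥ 3 and bilirubin ≥ 2, both children are listed. Any child with ALT or AST > 3 and bilirubin > 2 also satisfies the ≥ version, so the listing would contain everyone in the 11.4.2 combination row, provided the timing rule is the same. Section 11.4.2 lets the values come from different assessments; the 11.4.3 listing states no timing rule.

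**GGT, worked case.** Take peak GGT 6 and ALT 2.5, and assume AST and bilirubin meet no elevation row and no graded liver test reaches Grade 3. The child enters no multiple-of-ULN row and neither liver listing. The value does enter the visit summary and the shift table, and the PCS count and listing if the external criteria include GGT.

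**Why the other outputs do not supply a Grade 3+ count.** Shift tables stop at low, normal or high. PCS criteria are generally set at Grade 2 or higher (11.4.1), so a PCS count merges Grade 2 with Grades 3 and 4. PCS also requires a value more extreme than baseline, whereas the grade tables count regardless of baseline. Change-from-baseline summaries use the scheduled-visit value (SAP 6.5), so an unscheduled platelet low point would not be in them. An abnormal value must be recorded as an AE only if it is an SAE or leads to discontinuation of administration (Protocol 13.3), and the product is a single injection (Protocol 9.3).

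**Weight of one child.** Dose A has 3 children, Dose B 24 planned (12 + 12), Dose C 4 treated (SAP 2.2.1): 1/3 = 33%, 1/24 = 4%, 1/4 = 25%.

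**The case against.** The strongest reply is that little is actually hidden. An AST-led case with raised bilirubin is counted by dose in 11.4.2 and its values are listed there. Section 11.4.3 also promises that changes in ALT or AST relative to bilirubin will be assessed. Platelets and GGT receive visit summaries with minimum and maximum by dose, and with 3 or 4 children in Doses A and C the worst scheduled value is visible. Related Grade 3 or higher liver-enzyme events must be recorded whether or not serious (Protocol 13.1.3), related Grade III events go to the monitoring board, and SAP 11.3.2.5 tabulates AEs by maximum grade. The primary safety endpoints are AEs; laboratory tests are additional endpoints summarized descriptively.

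Most of this stands. It rules out a stronger reading that a reader might draw, namely that severe cases go untabulated by dose. For AST that is wrong. For platelets and GGT it goes too far, and because the PCS criteria are not in the documents, their absence from PCS cannot be asserted. Calling GGT a safety signal would also be too strong; the documents use it as an eligibility, taper and monitoring test.

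The reply does not remove the mismatch between the 11.4.3 listing and its own definition. Nor does it give a Grade 3+ laboratory count for platelets or GGT: the AE route misses values judged unrelated or never reported as events.

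**Conclusion.** The point holds in two limited parts. The Hy's Law listing contradicts the ALT-or-AST component in its own section and the combination row in 11.4.2. No case is lost from the analysis, but the listing meant to identify candidates can omit one. Separately, platelets and GGT have no Grade 3 or higher laboratory count by dose; platelets matter more, being both a named risk and an event of special interest.

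No numerical result in the plan changes. The size is that of one child in small groups: 33% of Dose A, 4% of the planned Dose B and 25% of Dose C. The conclusion assumes that PCS follows its general Grade 2 threshold; if the external criteria split grades for platelets and GGT, the second part largely falls away, and the SAP should say so. It is an alignment of outputs that should be made.

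**What to change.** In SAP 11.4.3, change the listing to select ALT or AST ≥ 3 × ULN with total bilirubin ≥ 2 × ULN. Keep the inclusive signs, which agree with the 3-fold-or-greater component, and state the same timing rule as the 11.4.2 combination row so that the listing contains every child counted there.

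In SAP 11.4.2, add platelets and GGT to the maximum-grade tables with rows for at least Grade 2 and at least Grade 3. Show GGT in both liver listings. Trigger the hematology listing on Grade 3 or higher platelets as well as on hemoglobin. No row at the 2 × ULN taper threshold is needed, since that is a management trigger and not a severity grade.

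The cost is a short SAP revision and a few table rows and listing columns from samples the protocol already collects.
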